GVP	EU Guideline on Good Pharmacovigilance Practices
HCP	health care provider
ICF	Informed Consent Form
ICH	International Conference on Harmonisation
IRB	Institutional Review Board
ISPE	International Society of Pharmacoepidemiology
JAK	janus kinase
LN	lupus nephritis
MPA	microscopic polyangiitis
NCI	National Cancer Institute
NO	Non-oncology conditions
NSAID	Non-steroidal anti-inflammatory drugs

Abbreviation	Definition	
PAC	Patient Alert Card	
PASS	post-authorization safety study	
PBRER	periodic benefit-risk evaluation reports	
PIL	Patient information leaflet	
PML	Progressive Multi-focal Leukoencephalopathy	
PRAC	Pharmacovigilance Risk Assessment Committee	
Q	Quarter	
QC	quality control	
RA	rheumatoid arthritis	
SAE	Serious adverse event	
SDV	Source data verification	
SLE	systemic lupus erythematosus	
SOP	Standard Operating Procedure	
SPC	Summary of Product Characteristics	
TNF	tumour necrosis factor	
UAT	user acceptance testing	
UK	United Kingdom	
US	United States	

2. RESPONSIBLE PARTIES

- Roche is the sole sponsor of the study. Scientists from Real World Data Science, Safety Science, Global Medical Affairs and Regulatory departments have collaborated in the design and will be responsible for evaluating the implications of the results to future patient and physician communications regarding MabThera® treatment in non-oncology indications.
- epidemiologists were the main party responsible for developing this protocol.
 epidemiologists have also contributed to the development of this protocol.
- a contract research organisation (CRO), will be responsible for the conduct, analysis and scientific oversight of the study. This will include site and physician recruitment, monitoring of sites for patient recruitment, data collection, cognitive pretesting and ethics committee submissions.
- Local investigators at each infusion centre will be responsible for abstraction of
 medical records and distribution of the self-administered patient questionnaire. If
 local investigators require support for medical record abstraction, support could be
 provided by However, medical record abstraction will be conducted
 always at the local site; medical record data, including patient identifiers, will never
 leave the infusion centre.
- The study team will be responsible for reporting any possible adverse drug events to the Roche local affiliate using the processes outlined in Section 10.
- Roche will assess the information for possible adverse events and product complaints (see Section 10) and forward for processing to the company safety database and/or to the Product Complaints group as applicable through Roche's usual processes and standard operating procedures.
- Roche will be responsible for fulfilling any responsibilities for reporting results to regulatory agencies.

Main Protocol Authors - F.Hoffmann-La Roche Ltd. F. Hoffmann-La Roche Ltd , Basel – Switzerland Telephone Email: F. Hoffmann-La Roche Ltd Basel – Switzerland Telephone

Main Protocol Authors - Research Triangle Institute, Spain Telephone+ Fax: E-mail: Main Protocol Authors France Telephone: United Kingdom Telephone:

3. **SYNOPSIS**

TITLE: MABTHERA DRUG UTILISATION STUDY AND PATIENT

ALERT CARD EVALUATION IN NON-ONCOLOGY PATIENTS IN EUROPE: AN INFUSION CENTRE-BASED APPROACH

PROTOCOL NUMBER: BA28478

VERSION NUMBER: 3.0

DATE OF PROTOCOL: 8 September 2015 **EU PAS REGISTER** To be determined

MEDICINAL PRODUCT: Rituximab (generic name); Mabthera® (brand name)

INTERNATIONAL MEDICAL

DIRECTOR:

MAIN AUTHOR:

NUMBER:

PHASE: IV, non-interventional study

INDICATION: Rheumatoid arthritis (RA); granulomatosis with polyangiitis

(GPA); microscopic polyangiitis (MPA)

MARKETING Roche Registration Ltd

AUTHORIZATION HOLDER: [name]

Rationale and Background

Rituximab (MabThera) received European Medicines Agency (EMA) approval in June 2006 for the treatment in combination with methotrexate of adult patients with severe, active RA who have had an inadequate response or intolerance to other disease-modifying anti-rheumatic drugs including one or more tumour necrosis factor (TNF) inhibitor therapies. In March 2013, the EMA approved a new non-oncology-related indication, allowing the use of MabThera in combination with glucocorticoids for the induction of remission in adult patients with severe, active GPA (Wegener's) and MPA. This protocol addresses the 2 European Union (EU) followup measures (FUMs) following approval of Variation EMEA/H/C/165/II/65 for MabThera use in RA (1) FUM no. 68 (Clinical). Drug Utilisation Study (DUS) to Assess Off-Label Use and (2) FUM No, 71.1 (Pharmacovigilance): Evaluation of Receipt, Use, and Impact of the Patient Alert Card (PAC) on Infections, Including Progressive Multi-focal Leukoencephalopathy (PML).

Research Question and Objectives

A single study is proposed to address both EU FUMs with the following objectives:

- 1. To quantify and characterise off-label use through an evaluation of the disease and characteristics of patients treated with MabThera for non-oncology conditions.
- 2. To evaluate the extent to which patients receive and read the PAC, knowledge of the PAC content among patients receiving MabThera for non-oncology conditions at infusion centres, and whether distribution of the PAC may influence patient actions.

Study Design

A geographically dispersed and diverse set of infusion centres in the United Kingdom (UK), Germany, France, Italy, and Spain will be recruited to participate in the study. At each participating centre, de-identified data will be retrospectively abstracted from medical records on non-oncology treatment indication and patient and disease characteristics for all patients receiving MabThera. In addition, a self-administered patient questionnaire will be employed to collect information on patient knowledge about the risk of infections including PML, patient receipt and review of the PAC, and any actions the patient has taken as a result of receiving the PAC.

Description of Study:

Data from medical records will be retrospectively abstracted over a 12-month look back period in the participating infusion centres. Patients will be recruited in the same infusion centres to participate in the patient survey during a 10-month data collection period.

Start Date of Study:

The study start date will be the date of the first data collection: the date on which information on the first study patient from the survey is recorded in the study database or, the date on which retrospective data extraction starts.

End of Study:

The end of the study will be the date on which the last information of the last patient is recorded in the study database.

Population

Patients must meet the following inclusion criteria for study entry:

- Patient is in the centre to receive an infusion for MabThera for a non-oncology indication during the study period
- · Patient is aged 18 years or older
- Patient provides informed consent for medical record abstraction and/or survey participation
- Patient participating in the survey can read and understand English, Spanish, Italian, French, or German, according to the country

No Exclusion criteria will apply for medical record abstraction participation although patients who meet any of the following criteria will be excluded from the survey participation:

- · Patient has previously already completed the MabThera survey
- Patient has participated in the past 12 months in a clinical trial in which MabThera was one of the treatments being evaluated

Variables

Medical record data:

- · Patient demographics
- · Indication for which MabThera has been prescribed
- Disease severity
- · Treatment history

Patient questionnaire data:

- · Patient demographics
- · Patient awareness of potential risk factors
- · Receipt and reading of the PAC

MabThera—F. Hoffmann-La Roche Ltd

· Additional safety-related materials

Data Sources

Patient medical records; self-administered patient questionnaire.

Study Size

Based on the results of a feasibility evaluation, it is estimated that 1,000-1,500 medical records of patients receiving MabThera will be abstracted during the study period and that 500-700 patients will complete the guestionnaire at participating infusion centres.

Data Analysis

Analysis of MabThera off-label use and evaluation of PAC knowledge and utilisation will be descriptive in nature and will entail the tabular display of summary statistics and the frequency distribution of item responses. A detailed analysis plan describing methods of analysis and presentation, as well as table shells, will be developed prior to starting analysis of data. All analyses will be performed using SAS 9.2 (or higher) statistical software (SAS Institute Inc., Cary, North Carolina, USA).

Milestones

Milestone	Planned Date	
Protocol approval by an IRB/EC	Q3 2015	
Start of data collection	Q4 2015	
End of data collection	Q3 2016	
Registration in the ENCePP EU PAS register	Q3 2015	
Final report of study results	Q2 2017	

4. PROTOCOL AMENDMENTS AND UPDATES

Protocol version 1.0: 27 July 2012 Protocol version 2.0: 24 June 2014 Protocol version 3.0: 8 September 2015

Protocol amendments/updates so far: see table below

Amendment/ Update Number	Date	Section of Study Protocol	Amendment or Update	Reason
2.0	24 June 2014	Background, on-label use definition, off- label use definition	Added information on addition to the Summary of Product Characteristics (SPC) of the indication for severe, active granulomatosis with polyangiitis (Wegener's) (GPA) or microscopic polyangiitis (MPA). Likewise, added to diseases defining onlabel use and deleted from the list of diseases defining offlabel use.	To reflect up- to-date approved indications
2.0	24 June 2014	Feasibility assessment, analysis and interpretation, strengths and limitations	The supplementary analysis of off-label use to be performed using existing registry data is no longer included as part of the study. References in the text to additional analysis of off-label use using registries data have been deleted.	The marketing authorisation holder has already completed activities, and others are ongoing, outside the scope of this study.

2.0	24 June 2014	Study population, patient eligibility for medical record abstraction, patient eligibility for survey participation, medical record abstraction, informed consent	The period of recruitment and implementation of the medical record abstraction component will be extended in France and Italy. The eligibility criterion of patient informed consent has been added as inclusion criteria for study patients in France and Italy. A specific process in France and Italy for obtaining patient informed consent in France and Italy to abstract their medical records is added to the text.	New local regulations in France and Italy require patient informed consent procedures for medical record abstraction.
2.0	24 June 2014	Patient eligibility for survey participation, medical record abstraction, strengths and limitations	A reference has been added to the plan for medical record abstraction recruitment logs in France and Italy. The text describing the use of recruiting log data to compare characteristics of study participants and non-participants has been changed to reflect that linking of survey and medical record	Linkage of data would require patient informed consent process.

			abstraction data will not take place during the study. References in the text to the use of linkage of medical record abstraction and survey data to compare characteristics of study participants and non-participants have been deleted.	
3.0	8 September 2015	Synopsis (Section 3) and Population (Section 8.2)	Patient eligibility criteria have been amended and now include an exclusion criteria section that only applies to participants who take part in the survey. The inclusion criteria now includes the following criterion: patient provides informed consent for medical record abstraction and/or survey participation.	Distinction between inclusion and exclusion criteria enhances clarity, and now the text reflects the updated consent requirements for patients i.e. patients in all countries will provide informed consent to participate in either/both components of the study.
3.0	8 September 2015	Overview of Study Design (Section 8.1.1)	Study design clarified to reflect that retrospective chart review of patient medical records will be performed within a 12-month period prior to the index date (start date of medical record	This study design will ensure that data collected are fully reflective of real-world use of MabThera and not influenced by study awareness.

			abstraction). The patient survey will be performed after the index start date.	
3.0	8 September 2015	Informed Consent (Section 9.2)	Informed consent is now required for either/both medical record abstraction and survey participation, in all study countries.	To reflect latest ethical requirements.
3.0	8 September 2015	Data Management - Electronic Case Report Forms (Section 8.7.2)	Text has been amended to indicate that both medical record data and patient questionnaire data will be abstracted into eCRF.	To clarify data management.

5. MILESTONES

Milestone	Planned Date
Protocol approval by an IRB/EC	Q3 2015
Start of data collection	Q4 2015
End of data collection	Q3 2016
Registration in the ENCePP EU PAS register	Q3 2015
Final report of study results	Q2 2017

6. RATIONALE AND BACKGROUND

6.1 RHEUMATOID ARTHRITIS, GRANULAMATOSIS WITH POLYANGIITIS, AND MICROSCOPIC POLYANGIITIS

Rheumatoid arthritis (RA) is a chronic autoimmune disease characterised by inflammation of the membrane lining the joints (the synovium) (Klarenbeek et al. 2010). The inflamed synovium causes a loss of joint shape, function, and alignment that can eventually lead to complete destruction of the involved joints. Patients with RA have pain, redness, swelling, stiffness, and restricted movement around the joints of the hands, feet, elbows, knees, and neck that lead to loss of function and deformity. Additional common manifestations of RA include fatigue, anaemia, and osteoporosis. Extra-articular manifestations of RA may affect major organ systems, and along with complications of long-term treatment, can lead to a decreased life expectancy.

Approximately 2.8 million Europeans are affected by RA (Alamanos et al. 2006), and more than 20 million people are affected worldwide (Business Wire, 2004). The prevalence of RA is higher in women than in men, and estimates of the prevalence from European studies range from 1 to 6 cases per 1,000 men and 3 to 12 cases per 1,000 women (European Commission, 2010). Southern European countries have lower median incidence and prevalence rates than northern European countries (Alamanos et al. 2006).

Granulomatosis with polyangiitis (GPA) and microscopic polyangiitis (MPA) are rare small-vessel vasculitides that are characterized by the presence of circulating antineutrophil cytoplasmic autoantibodies (ANCAs) in 80–94% of affected patients (Finkielman et al. 2007; Guillevin et al. 1999). The prevalence of ANCA-associated vasculitis (AAV) has increased in recent years, in part due to increased recognition of these complex diseases. AAVs have an annual incidence of 20 per million population (Ntatsaki et al. 2010). GPA and MPA are severe, progressive diseases that, left untreated, can lead to death from multisystem organ failure. Disease recurrence and drug-related toxicity continue to produce significant morbidity and mortality, and remain the main challenges in patient management (Hoffman et al. 1992).

6.2 MABTHERA

Rituximab (MabThera®) is a genetically engineered chimeric murine/human monoclonal antibody, which binds specifically to CD20, a B-lymphocyte differentiation antigen on pre-B and mature B-lymphocytes. In June 2006, the United States (US) Food and Drug Administration had approved MabThera for RA (Food and Drug Administration, 2006). In June 2006, the European Medicines Agency (EMA) approved the use of rituximab for the same indication. The RA indication was updated by Variation EMEA/H/C/165/II/65 (EMA, 2010). The current European Union (EU) approved label authorises MabThera in combination with methotrexate for the treatment of adult patients with severe, active RA who have had an inadequate response or intolerance to other disease-modifying anti-rheumatic drugs including one or more tumour necrosis factor (TNF) inhibitor therapies.

In March 2013, the EMA approved a new non-oncology-related indication, allowing the use of MabThera in combination with glucocorticoids for the induction of remission in adult patients with severe, active GPA (Wegener's) and MPA (EMA, 2013a). Rituximab is also approved for several oncology conditions, but these indications are not the focus of this study.

This protocol addresses the 2 EU follow-up measures (FUMs) following approval of Variation EMEA/H/C/165/II/65 for MabThera use in RA.

1. FUM no. 68 (Clinical): Drug Utilisation Study to Assess Off-Label Use

There is concern regarding off-label use of MabThera, in particular that rheumatologists and other physicians may prescribe MabThera for systemic lupus erythematosus (SLE) and lupus nephritis (LN). The EMA Committee for Medicinal Products for Human Use (CHMP) FUM (Clinical) No. 68 from Procedure No. EMEA/H/C/165/II/65 states, 'Given the extensive off-label potential of MabThera, the MAH [Marketing Authorisation Holder] should submit a European drug utilisation study protocol to the CHMP'.

2. FUM No, 71.1 (Pharmacovigilance): Evaluation of Receipt, Use, and Impact of the Patient Alert Card (PAC) on Infections, Including Progressive Multi-focal Leukoencephalopathy (PML)

As with other immunomodulatory therapies, MabThera use may carry a risk of developing progressive multi-focal leukoencephalopathy (PML). PML is a rare but serious and potentially fatal viral disease characterised by progressive damage of the white matter at multiple locations in the brain. Roche currently provides physicians with PACs to distribute to non-oncology patients to inform them of this potential risk, of risk of infections in general, and of signs and symptoms that should prompt them to seek medical care. In addition, alert cards are supplied in MabThera cartons, attached to the patient information leaflet (PIL).

The PAC text is identical in both the locally distributed PACs and the in-carton PACs, although the appearance of the 2 cards may differ in certain EU Member States, depending on the layout of the locally distributed PAC. It should be noted that the format of the in-carton PAC may be subject to change during the set-up period for this study. EMA will be notified of any change made. No change to the PAC text is foreseen. The PAC version distributed to patients in this study is dependent on distribution by Roche of the non-oncology PAC to centres prior to the study start date. The text for the non-oncology PAC is in Appendix 1. The EMA CHMP FUM (Pharmacovigilance) No. 71.1 in Procedure No. EMEA/H/C/165/II/65 requests:

"... submission of a proposal to conduct patient and physician user acceptance testing of the PML AC [alert card] and an assessment of the proportion of patients who receive the card, who use it, who use it correctly and whose outcome is improved by the card. This assessment should include reporting milestones."

The User Acceptance Testing (UAT) part of this FUM has already been addressed. The results submitted to EMA in July 2012 and, following EMA endorsement, the resulting text changes were updated into the Product Information Annex IIIA during the Variation EMEA/H/C/65/II/89 approved in April 2014. This study protocol is designed to assess the PAC for its current distribution to patients with RA, GPA and MPA.

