7. RESEARCH QUESTION AND OBJECTIVES

7.1 OBJECTIVES

- Specific aim 1: To quantify and characterise off-label use through an evaluation of the disease and characteristics of patients treated with MabThera for non-oncology conditions.
- Specific aim 2: To evaluate the extent to which patients receive and read the PAC, knowledge of the PAC content among patients receiving MabThera for nononcology conditions at infusion centres, and whether distribution of the PAC may influence patient actions.

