8.2 POPULATION

Infusion centres that are representative of the non-oncology use of MabThera in the UK, Germany, France, Italy, and Spain will be recruited to participate in the study. Each centre will be expected to retrospectively abstract data from medical records for non-oncology MabThera patients and to enrol an appropriate number of patients who will complete the patient questionnaire component of the study; the target is a total of 100 survey participants per country. The survey participants will be recruited during a 10-month period concomitantly with the medical record abstraction process.

Infusion Centre Eligibility

To participate in the study (DUS and PAC survey), each infusion centre must meet all of the following criteria:

- 1. Administer MabThera to a least 20 patients who would meet the eligibility criteria in the past 12 months; and
- 2. Be able to provide a semi-private space for patient recruitment, the consent process, and completion of the patient questionnaire; and
- Have a staff member available to coordinate study activities.

Patient Eligibility for the study

Patients must meet the following inclusion criteria for study entry:

- 1. Patient is in the centre to receive an infusion for MabThera for a non-oncology indication during the study period
- 2. Patient is aged 18 years or older
- Patient provides informed consent for medical record abstraction and/or survey participation
- 4. Patient participating in the survey can read and understand English, Spanish, Italian, French, or German, according to the country.

No Exclusion criteria will apply for medical record abstraction participation although patients who meet any of the following criteria will be excluded from the survey participation:

- 1. Patient has previously already completed the MabThera survey
- 2. Patient has participated in the past 12 months in a clinical trial in which MabThera was one of the treatments being evaluated.

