
Patient Alert Card Distribution

The PAC will be distributed to all patients receiving MabThera for non-oncology indications, as stated on the card.

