To evaluate the differences between subgroups by indication, with 95% CIs, proportions for categorical variables and means for continuous variables will be estimated within each subgroup. If appropriate, medians will be used instead of means when the variables of interest do not assume a normal distribution.

It is anticipated that the analyses of the PAC knowledge and utilisation will focus on summarising the results of the questionnaire data (e.g., percentage confirming receipt of the PAC, percentage demonstrating correct knowledge of the PAC, percentage correctly identifying the appropriate actions they should take under different scenarios). Tables will include frequencies and percentages for categorical variables and descriptive statistics (e.g., median, means and standard deviations or 95% CIs) for continuous variables (e.g., scales or composite variables created from summation of several items). Results will be grouped by key variables that could be related to patient awareness, such as recency of the first treatment with MabThera and whether the participant reported reading the PAC. Results will also be grouped by the clinical condition for which the patient received MabThera (RA, other autoimmune diseases) in a subset of patients who provided consent for both the questionnaire and medical record abstraction (since information on clinical condition is only provided by the latter). Open-ended responses (if any) will be listed and categorised as appropriate, but will not be analysed quantitatively. In the study report, results will be provided in aggregate form only.

The number of patients who were invited to participate in the survey but declined will be tracked, and the analyses will describe selected key general characteristics of non-respondents (e.g., reason for refusal). Based on the information available on the recruiting logs (i.e., age, sex, and clinical indication), the analysis will compare characteristics of survey respondents with characteristics of patients who refused to participate in the survey. Also, characteristics of the infusion centres participating in the study will be compared with characteristics of the overall set of infusion centres from the final list of infusion centre used, based on the information available for all centres on the list, e.g., geographic location, centre type (clinic, hospital), and physician specialty (internal medicine, rheumatology).

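### Section 6.2 and aim 2 name different populations for the card assessment, and the survey grouping by disease in Section 8.6 does not follow the protocol's own on-label definition.

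*Protocol*

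**What the plan says.** Section 6.2 describes the card population in two ways. Early on it states "Roche currently provides physicians with PACs to distribute to non-oncology patients"; its last sentence is "This study protocol is designed to assess the PAC for its current distribution to patients with RA, GPA and MPA".

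The operative sections use the wider population:
- Aim 2 (Section 7.1): "knowledge of the PAC content among patients receiving MabThera for nononcology conditions at infusion centres".
- Eligibility (Section 8.2): "Patient is in the centre to receive an infusion for MabThera for a non-oncology indication during the study period".
- Card distribution (Section 8.2): "The PAC will be distributed to all patients receiving MabThera for non-oncology indications, as stated on the card".
- The card text in Appendix 1 is addressed to patients with non-oncology diseases.

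Section 8.3 defines off-label use as a non-oncology condition other than RA and GPA/MPA.

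For the survey, Section 8.6 plans summaries such as "percentage confirming receipt of the PAC" and one split by disease: "Results will also be grouped by the clinical condition for which the patient received MabThera (RA, other autoimmune diseases) in a subset of patients". The subset is those who consented to both the questionnaire and the record abstraction, because disease comes only from the record. Section 8.2 lets a patient take part in the survey alone. The draft questionnaire does not ask which disease is treated; its demographic items are age, sex and education.

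**The concern.** The regulator's request quoted in Section 6.2 asks what proportion of patients receive and use the card, and the answer depends on which patients are counted. The protocol gives two populations, which differ by every condition that Section 8.3 lists as potentially off-label.

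The disease split in Section 8.6 does not bridge them. It separates RA from everything else, whereas the protocol's label boundary runs between RA plus GPA/MPA and everything else. A shortfall in the second group could therefore sit in on-label vasculitis patients or in off-label patients, and the planned table would not show which. Section 8.6 says the results may lead to changes in the card programme, and the two explanations would point to different changes. For patients who join only the survey, a disease not asked at the visit cannot be recovered afterwards.

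**Working it through.** **1. Two classifications side by side**

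| Disease | Section 8.3 | Survey grouping in 8.6 (plain reading) |
|---|---|---|
| RA | on-label | RA |
| GPA/MPA | on-label | other autoimmune diseases |
| SLE, myopathies, Sjögren syndrome and others | off-label | other autoimmune diseases |

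The RA group is entirely on-label by disease. The second group mixes both classes, so neither the on-label nor the off-label figure can be read from the two groups.

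**2. What the collected data allow**

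- *Both consents:* the abstraction form has a separate GPA/MPA category (Section 8.3, Appendix 1). On-label and off-label results can be derived without new data.
- *Survey only:* disease is unknown. The recruitment logs may hold the indication, but they carry no patient identifier and are kept separately by component (Section 8.2), and survey data are not linked to any log (Section 9.4).

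**3. The protocol's own precision, reproduced**

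Half-width = 1.96 × √(p(1−p) × DE / n), with DE = 1 + (m−1) × ICC and m = 8 (Section 8.5, Table 1).

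- p = 75%, n = 500, ICC 0: 1.96 × √(0.75 × 0.25 / 500) = 3.8 points, giving 71.2% to 78.8%, as stated.
- ICC 0.3: DE = 1 + 7 × 0.3 = 3.1; 3.80 × √3.1 = 6.7 points, giving 68.3% to 81.7%, as stated.

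All 36 rows of Table 1 reproduce to 0.1 point.

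**4. How far the pooled and on-label figures can differ**

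Pooled = (1 − s) × on-label receipt + s × off-label receipt, where s is the off-label share of respondents. The difference in size is therefore s × receipt gap. The protocol gives neither quantity, so both are assumed:

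| Off-label share | Gap 10 points | Gap 20 points | Gap 30 points |
|---|---|---|---|
| 10% | 1.0 | 2.0 | 3.0 |
| 25% | 2.5 | 5.0 | 7.5 |
| 50% | 5.0 | 10.0 | 15.0 |

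**5. Precision of an on-label result**

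The protocol gives neither the on-label share nor the dual-consent rate. Assume an on-label share of 50-90% and dual consent of 50-100% among 500 surveys. Then n runs from 500 × 0.5 × 0.5 = 125 to 500 × 0.9 × 1 = 450. At 75% receipt the half-width is 7.6 down to 4.0 points with ICC 0, and 13.4 down to 7.0 points with DE 3.1.

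What classifying every respondent gains, at an assumed 75% on-label share:
- Half with dual consent, n = 187.5: ±6.2 points (ICC 0) or ±10.9 (DE 3.1).
- All classified, n = 375: ±4.4 points (70.6% to 79.4%) or ±7.7 (67.3% to 82.7%).

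GPA/MPA alone stays imprecise. For an assumed share of 5-20% of 500 (n = 25 to 100), the half-width is 17.0 to 8.5 points even with ICC 0.

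**The case against.** The strongest reply is that the pooled population is the right one. Aim 2, eligibility, the distribution rule and the card's own heading all say non-oncology patients, and the regulator's quoted request is not limited to labelled diseases. One closing sentence in a background section does not set the target. This stands: pooling is not a defect, and it is 6.2 that should change.

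A reader might infer that card receipt in RA, GPA and MPA patients can never be estimated. The documents do not support that. RA is a planned group, GPA/MPA is recorded separately, and in patients with both consents the on-label figure is a recombination of existing categories.

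A reader might also infer that the pooled figure will clearly miss the on-label rate. Take 75% on-label with 80% against 50% receipt: 0.75 × 80 + 0.25 × 50 = 72.5%, with a half-width of 3.9 points if clustering is ignored. The two receipt rates have no source in the protocol, and the 75% is a precision illustration in Section 8.5, not a prevalence. With DE 3.1 the half-width is 3.9 × √3.1 = 6.9 points (65.6% to 79.4%), which only just excludes 80%. With 60% in off-label patients the pooled figure is 75.0% (68.3% to 81.7%), which includes it.

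It can also be said that Section 8.6 leaves subgroup analysis to a later plan and that its two-group parenthesis is brief. That GPA/MPA falls in the second group is indeed a reading, since the text does not say so outright. But 8.6 itself fixes the grouping and its restriction to dual-consent patients, and no analysis plan can supply a disease that was not collected.

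**Conclusion.** The point holds as an inconsistency with a practical consequence. Section 6.2 disagrees with aim 2 and Section 8.2 on whom the card assessment concerns, and the passages must be reconciled. The only disease grouping stated for the survey cuts across the on-label definition in Section 8.3, so no planned survey result is for on-label or off-label patients, and survey-only respondents cannot be classified at all.

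The size is unknown. The range of 1 to 15 points rests wholly on assumed off-label shares of 10-50% and receipt gaps of 10-30 points, and nothing in the protocol shows that receipt differs by label status. It is the distance between two legitimate quantities and not a bias in the pooled estimate, which answers aim 2. Any interval set beside it should carry the protocol's clustering, with a design effect of up to 3.1 in Table 1. The change is worth making because it is cheap now and cannot be made later for survey-only patients.

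**What to change.** 1. Reword the last sentence of Section 6.2 so that the card assessment covers patients receiving MabThera for non-oncology conditions, as in aim 2 and Section 8.2.
2. In Section 8.6, replace the two-way survey grouping by RA, GPA/MPA and other (off-label). Report card receipt, reading and knowledge for RA and GPA/MPA combined, for other conditions, and overall. Give intervals that allow for clustering by centre.
3. Add one closed item to the draft questionnaire asking for which disease MabThera is given: RA; GPA (Wegener's) or MPA; other; don't know. Use the record diagnosis where it is available and the questionnaire answer for survey-only respondents, and state how many were classified by each route.

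The cost is one item in a questionnaire that Section 8.3 already leaves open to change after cognitive testing, one changed table grouping and one reworded sentence. Self-reported disease is less exact than the record; patients with both sources allow agreement to be checked. Subgroup intervals will be wider than the overall one, and GPA/MPA on its own may be too small for more than description.
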